9.3.1 Pharmacokinetic Analyses

9.3.1.1 Descriptive Statistics

The plasma and urine MK-8527 and PBMC MK-8527-TP concentrations and the PK parameters listed in [Section 8.3.2](#) and [Section 8.3.4](#) will be summarized using the appropriate descriptive statistics which will be fully outlined in the SAP.

9.3.1.2 Renal Function Categorization

For study eligibility and primary analysis, participants will be categorized using de-indexed eGFR values (with eGFR expressed as mL/min) calculated at screening.

For additional analyses, participants will also be re-categorized into renal function groups using indexed eGFR values from the 2021 CKD-EPI creatinine equation (with eGFR expressed as mL/min/1.73 m²), calculated from values collected at screening.

Summary Statistics using De-indexed eGFR

The participants will be categorized into different renal categories based on their de-indexed eGFR. Non-model based summary statistics by population will be provided for plasma MK-8527 AUC₀-last, AUC₀-inf, C_{max}, T_{max}, t_{1/2}, CL/F, and V_z/F, and for PBMC MK-8527 AUC₀-last, AUC₀-inf, C_{max}, C₁₆₈, C₆₇₂, T_{max}, and t_{1/2}.

Summary Statistics using the 2021 CKD-EPI Creatinine Equation

The participants will be re-categorized into different renal categories based on their indexed eGFR calculated using the 2021 CKD-EPI creatinine equation. Non-model based summary statistics by population will be provided for plasma MK-8527 AUC₀-last, AUC₀-inf, C_{max}, T_{max}, t_{1/2}, CL/F, and V_z/F, and for PBMC MK-8527-TP AUC₀-last, AUC₀-inf, C_{max}, C₁₆₈, C₆₇₂, T_{max}, and t_{1/2}.

9.3.1.3 Statistical Analyses for Plasma MK-8527 and PBMC MK-8527-TP

Separately for each PK parameter, individual values of plasma MK-8527 AUC0-last, AUC0-inf, and Cmax, of PBMC MK-8527-TP AUC0-last, AUC0-inf, Cmax, C168, and C672, after a single-dose administration of MK-8527 to participants with severe and moderate RI and to healthy control participants will be ln-transformed and evaluated with a linear fixed effects model containing a categorical effect for population (participants with severe RI, with moderate RI, and healthy control participants). An unstructured covariance matrix will be used to allow for unequal population variances via the REPEATED and GROUP statement in SAS PROC MIXED. Kenward and Roger's method will be used to calculate the denominator degrees of freedom for the fixed effect (DDFM=KR). Ninety-five percent (95%) CIs for the least-squares means (LSM) for each population will be constructed on the ln scale and will reference the t-distribution. Exponentiating the LSM and their corresponding 95% confidence limits will yield estimates for the population geometric means and CIs about the geometric means on the original scale.

Sample SAS code is given below:

```
proc mixed data=data;  
class population ;  
model lnpk = population /ddfm=kr;  
repeated/ group= population type=UN;  
lsmeans population /cl alpha=0.05;  
run;
```

To address the primary and secondary estimation objectives and compare participants with severe RI or moderate RI to healthy control participants with normal renal function, a two-sided 90% CI for the true difference in means (participants with severe RI – healthy control participants) and true difference in means (participants with moderate RI – healthy control participants) will be calculated for each PK parameter using the mean square error from the model and referencing a t-distribution. These confidence limits will be exponentiated to obtain the 90% CI for the true ratio of geometric means (participants with severe RI/healthy control participants) and (participants with moderate RI/healthy control participants) for each PK parameter.

Individual values will be listed for each PK parameter (plasma MK-8527 AUC0-last, AUC0-inf, Cmax, Tmax, t_{1/2}, CL/F, and Vz/F; PBMC MK-8527-TP AUC0-last, AUC0-inf, Cmax, C168, C672, Tmax, and t_{1/2}) by population, and the following (non-model-based) descriptive statistics will be provided: n (number of participants with non-missing data), arithmetic mean, standard deviation, arithmetic percent coefficient of variation (CV; calculated as 100 x standard deviation/arithmetic mean), median, minimum, maximum, geometric mean, and geometric percent CV (calculated as 100 x sqrt(exp(s²) - 1), where s² is the observed variance on the ln scale).

Figures showing individual PK values with geometric means (95% CIs) by population, plotted on the ln scale, will be provided for plasma MK-8527 AUC0-last, AUC0-inf, and Cmax, and for PBMC MK-8527-TP AUC0-last, AUC0-inf, Cmax, C168, and C672.

Individual participant PK values will also be plotted against indexed eGFR using each individual's BSA, using different symbols to identify participants from each population. For this analysis, eGFR will be calculated as the mean of the two values determined at screening.

Additionally, plots of PK parameter values versus age, BMI, and/or sex may be provided.

Statistical modelling of the relationship between renal function (based on de-indexed eGFR) and PK parameters using linear (and non-linear as appropriate) regression analysis of eGFR versus AUC and Cmax (total and unbound) may be performed.

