9.1 Sample Size Determination

The between-participant standard deviations (on the natural log [ln] scale) for plasma MK-8527 AUC_{0-inf} and C_{max}, and for PBMC MK-8527-TP AUC_{0-inf} and C_{max} after administration of MK-8527 observed in a previous study (MK-8527-003) are 0.253 ln(h*nmol/L), 0.313 ln(nmol/L), 0.213 ln(h*pmol/10⁶ cells) and 0.262 ln(pmol/10⁶ cells), respectively. Assuming the same variability for 6 mg MK-8527, with 6 severe RI participants, 6 moderate RI participants, and 6 healthy participants, the half-width of the 90% confidence intervals (CIs) of geometric mean ratios (GMRs) for plasma MK-8527 AUC_{0-inf} and C_{max}, and for PBMC MK-8527-TP AUC_{0-inf} and C_{max} on the log scale will be 0.196, 0.242, 0.165, and 0.203 respectively. The lower and upper 90% confidence limits for the true GMRs will be given by OBS/1.21 and OBS*1.21 for plasma MK-8527 AUC_{0-inf}, OBS/1.27, and OBS*1.27 for plasma MK-8527 C_{max}, OBS/1.18 and OBS*1.18 for AUC_{0-inf} MK-8527-TP in PBMC, OBS/1.22, and OBS*1.22 for C_{max} MK-8527-TP in PBMC, where OBS is the observed least squares geometric mean ratio.

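### Section 9.3.1.3 gives two incompatible variance rules for the 90% GMR intervals: a separate-variance model, then a single mean square error that this model does not produce

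*Combined protocol and SAP*

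**What the plan says.** Protocol section 9.3.1.3 covers the ln-transformed plasma MK-8527 parameters (primary) and the PBMC MK-8527-TP parameters (secondary). Its statements on variance are these.

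- The model: "An unstructured covariance matrix will be used to allow for unequal population variances via the REPEATED and GROUP statement in SAS PROC MIXED". The sample code implements this as "repeated/ group= population type=UN".
- The degrees of freedom: "Kenward and Roger's method will be used to calculate the denominator degrees of freedom for the fixed effect".
- The intervals that answer the estimation objectives: "a two-sided 90% CI for the true difference in means", for severe minus healthy and moderate minus healthy. These "will be calculated for each PK parameter using the mean square error from the model and referencing a t-distribution". That sentence gives no df.
- The only interval requested in the sample code: "lsmeans population /cl alpha=0.05". This yields the 95% intervals for the group means. No line produces the 90% contrasts.

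Section 9.3 leaves detailed methodology to a separate SAP. Nothing else in the document says which variance the contrast intervals use.

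**The concern.** A mean square error is one residual variance pooled over all groups. The model described two paragraphs earlier has three residual variances and no pooled one. An analyst who follows the model paragraph takes the standard error from the two groups being compared, with a df specific to that contrast. An analyst who follows the contrast sentence pools all three groups on 18 − 3 = 15 df. These intervals differ.

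The study has no hypothesis test (section 9.3.1.5), so the geometric mean ratio with its 90% interval is the primary inferential result. With 6 participants per group, the choice of variance can change the interval noticeably. If the text is left as it is, the choice could be made after the data are seen, in an open-label study.

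**Working it through.** **Inputs.** From section 9.1: 6 participants per group, and ln-scale SDs of 0.253 and 0.313 (plasma AUC0-inf and Cmax) and 0.213 and 0.262 (MK-8527-TP AUC0-inf and Cmax), all from a previous study. No SD for renal impairment is given. The SD ratios below are therefore assumptions, with the healthy SD fixed at 0.253.

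**The plan's own half-widths.** Section 9.1 states 0.196, 0.242, 0.165 and 0.203. The formula is t × SD × √(1/6 + 1/6). Of the critical values tried, only t(0.90, 15 df) = 1.3406 reproduces all four: 0.1958, 0.2423, 0.1649, 0.2028. That quantile belongs to a two-sided 80% interval, which is a separate matter. What counts here is the 15 df, a three-group pooled value. With the 90% quantile, the AUC0-inf half-width at SD 0.253 is:

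- pooled, 15 df: 1.7531 × 0.253 × 0.5774 = 0.256
- separate variances that happen to be equal, 10 df: 1.8125 × 0.253 × 0.5774 = 0.265

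**The two rules for severe/healthy.**

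- Pooled: MSE = (v_H + v_M + v_S)/3; half-width = t(0.95, 15) × √(2 × MSE/6).
- Separate: half-width = t(0.95, df*) × √(v_S/6 + v_H/6), with Satterthwaite df* standing in for Kenward-Roger in this one-way layout.

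**Direction of the error.** Let the SDs be in the ratio 1 : m : s (healthy : moderate : severe). For severe/healthy, the expected pooled variance of the difference, divided by the true one, is [2(1 + m² + s²)/3] / (1 + s²). This is below 1 only when m² < (1 + s²)/2, that is, when the moderate variance is below the average of the healthy and severe variances. For moderate/healthy, exchange m and s. Examples for severe/healthy:

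- 1:1:2 gives 4/5 = 0.80
- 1:1.5:2 gives 4.83/5 = 0.97
- 1:2:2 gives 6/5 = 1.20

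**Coverage of the nominal 90% interval** (simulation, 1,000,000 or more trials per row, 6 per group):

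| SD ratio H:M:S | Pooled, severe/healthy | Pooled, moderate/healthy | Separate variances |
|---|---|---|---|
| 1:1:1 | 90.0% | 90.0% | 90–91% |
| 1:1:1.5 | 87.5% | 94.3% | 90–91% |
| 1:1:2 | 85.4% | 96.9% | 90–91% |
| 1:1.5:2 | 89.0% | 94.7% | 90–91% |
| 1:1.5:1.5 | 91.6% | 91.6% | 90–91% |
| 1:2:2 | 92.2% | 92.2% | 90–91% |

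**Width.** At 1:1:2 the mean pooled half-width is 0.354 for both contrasts. Separate variances give 0.423 for severe/healthy and 0.263 for moderate/healthy. The pooled interval is thus 1 − 0.354/0.423 = 16% narrower for severe and 0.354/0.263 − 1 = 35% wider for moderate.

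**The case against.** The strongest reply is that the sentence refers to the error of the model just specified. That model is heteroscedastic, and the section describes no second, equal-variance model. On this reading the phrase is a loose label for the model-based standard error, coverage is about 90%, and no result changes. The reading is reasonable and cannot be excluded. It is not certain either, because the planning figures in section 9.1 rest on a pooled 15 df. But those figures are planning arithmetic under a common SD and do not instruct the analysis. A reader might infer that the plan has committed itself to a pooled interval; the documents do not establish that.

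A reader might also infer that pooling always makes the interval too narrow for the noisier group. The documents give no variance pattern to support this, and the table shows that it is not generally true. When both impaired groups are equally more variable, both pooled intervals are mildly conservative. With graded variability (1:1.5:2), severe/healthy is close to nominal.

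Two further points in the plan's favour stand. The point estimates are the same under either rule, because in this one-way model each is a difference of group means. Section 9 sets no equivalence or no-effect margin, so no formal decision depends on the interval.

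The sample code is labelled as a sample and does implement the 95% intervals of the paragraph above it. The missing contrast line is incompleteness rather than error. The REPEATED statement also has no SUBJECT= option, but no effect of that on the results has been tested, and the point does not rely on it.

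**Conclusion.** The inconsistency is certain: section 9.3.1.3 specifies group-specific variances and then takes the contrast intervals from a single variance that the model does not produce. Neither the sample code nor any other section resolves it.

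The numerical consequence is conditional. It needs the literal pooled reading and also unequal variances. Over the assumed patterns in the table, pooled coverage runs from 85.4% to 92.2% for severe/healthy and from 90.0% to 96.9% for moderate/healthy, and the direction depends on the pattern. With equal variances there is no coverage error.

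This should be fixed, because it governs the primary intervals and two careful analysts could report different ones. It does not reach the level of a must-fix.

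**What to change.** In section 9.3.1.3, replace the reference to the mean square error with: using the standard error of the difference from the separate-variance model and its Kenward-Roger degrees of freedom. Add a matching statement to the sample code for the two contrasts against healthy controls, either a DIFF option on LSMEANS or two ESTIMATE statements, with CL and alpha=0.10. Carry the same wording into the SAP before database lock.

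The cost is one sentence and one or two lines of code. The statistical cost arises if the variances are in fact equal: the mean AUC0-inf half-width then rises from about 0.252 to 0.263, about 4% (0.263/0.252 = 1.04).

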9.3.1.4 Statistical Analysis for Urine MK-8527

The amount of MK-8527 excreted in the urine collection interval from the time of dosing through 48 hours (Ae0-48) will be determined from the urine concentration and volume data. The fraction, fe, of MK-8527 excreted in urine expressed as a % MK-8527 administered dose will be determined. CLr of MK-8527 will be calculated from the urine Ae and plasma AUC available for the same time period (e.g., Ae0-48 and AUC0-48). Urinary drug clearance for each urine collection interval will be calculated for each group (with de-indexed eGFR expressed as mL/min). A descriptive summary of MK-8527 urine collection may be provided.

9.3.1.5 Multiplicity

There is no pre-specified hypothesis; therefore, no multiplicity adjustment is needed.

9.3.2 Safety Analyses

AEs will be coded using the most current version of Medical Dictionary for Regulatory Activities available at Celerion and summarized by group for the number of participants reporting the TEAE and the number of TEAEs reported. A by-participant AE data listing including verbatim term, coded term, treatment, severity, action, and relationship to treatment will be provided.

Safety data including clinical laboratory results, immunophenotyping results, vital sign assessments, and 12-lead ECGs will be summarized by time point of collection.

Quantitative safety data as well as the change from baseline, when appropriate, will be summarized using the appropriate descriptive statistics.

Concomitant medications will be listed by participant and coded using the most current version of World Health Organization Drug Dictionary available at Celerion.

Medical history will be listed by participant.

9.3.3 Interim Analysis

Not applicable.

10 STUDY ADMINISTRATION

10.1 Ethics

10.1.1 Institutional Review Board

This protocol will be reviewed by an IRB and the study will not start until the IRB has approved the protocol or a modification thereof. The IRB is constituted and operates in accordance with the principles and requirements described in the US Code of Federal Regulations (21 CFR Part 56). The IRB is ICH compliant.

10.1.2 Ethical Conduct of the Study

This research will be carried out in accordance with the protocol, US Code of Federal Regulations, 21 CFR Parts 50, 56, and 312, the ethical principles set forth in the Declaration of Helsinki, GCP, and the ICH harmonized tripartite guideline regarding GCP (E6[R2] Good Clinical Practice: Integrated Addendum to E6 [R1], November 2016).

10.1.3 Participant Informed Consent

The purpose of the study, the procedures to be carried out and the potential hazards will be described to the participants in non-technical terms. Participants will be required to read, sign and date an ICF summarizing the discussion prior to screening, and will be assured that they may withdraw from the study at any time without jeopardizing their medical care.

10.1.3.1 General Informed Consent

Informed consent given by the participant must be documented on a consent form. The form must include the study protocol number, study protocol title, dated signature, and agreement of the participant and of the person conducting the consent discussion.

A copy of the signed and dated ICF will be given to the participant before participating in the study, or FBR.

The initial ICF, any subsequent revised ICF, and any written information provided to the participant must receive the IRB's approval/favorable opinion in advance of use. The participant or his/her legally acceptable representative should be informed in a timely manner if new information becomes available that may be relevant to the participant's willingness to continue participation in the study. The communication of this information will be provided and documented via a revised consent form or addendum to the original consent form that captures the participant's or the participant's legally acceptable representative's dated signature.

Specifics about the study and the study population are to be included in the study informed consent form.

Informed consent will adhere to IRB requirements, applicable laws and regulations, and Sponsor requirements.

10.1.3.2 Consent and Collection of Specimens for Future Biomedical Research

The PI or designee will explain the FBR consent to the participant, answer all of his/her questions, and obtain documented informed consent before performing any procedure related to FBR.

A copy of the signed and dated informed consent will be given to the participant before performing any procedure related to FBR.

10.1.4 Confidentiality

All clinical sites and vendors will have signed confidentiality agreements with Celerion. By signing this protocol, the PI and CRU staff will regard all information provided by the Sponsor and all information obtained during the course of the study as confidential.

The clinical site and Celerion must guarantee the privacy of the participants taking part in the study. Participants will be identified throughout documentation and evaluation by a unique participant study number. Throughout the study, a participant's source data will only be linked to the Sponsor's clinical study database or documentation via a unique identification number. If participant name appears on any study document, it must be redacted before the copy of the documents is supplied to the Sponsor. Any information concerning the participants (clinical notes, identification numbers, etc.) must be kept on file by the PI or designee who will ensure that it is revealed only to the Sponsor, IRB, or regulatory authorities for the purposes of trial monitoring, auditing or official inspections. As required, in the case of an event where medical expenses are the responsibility of the Sponsor, personal information i.e., full name, social security details etc. may be released to the Sponsor. Appropriate precautions will be taken to maintain confidentiality of medical records and personal information in strictest confidence and in accordance with local data protection laws.

10.2 Study Termination

The CRU(s) reserves the right to terminate the study in the interest of participant welfare.

The Sponsor reserves the right to suspend or terminate the study at any time.

10.3 Data Management

Data management activities will be detailed in the Data Management Plan (DMP). Each vendor involved with this study will adhere to Good Documentation Practices and their standard operating procedures covering their respective activities relevant to participation in this study, as applicable. The PI or designee will ensure that all data related to the conduct of this study is attributable, legible, contemporaneous, original, accurate, enduring, and readily accessible.

Standard operating procedures are available for all activities performed at the CRU relevant to the quality of this study. Designated personnel of the CRU will be responsible for implementing and maintaining quality assurance (QA) and quality control systems to ensure that the study is conducted, and that data are generated, documented and reported in compliance with the study protocol, and GCP requirements as well as applicable regulatory requirements and local laws, rules and regulations relating to the conduct of the clinical study.

The Clinical Study Report will be audited by the QA department and the QA audit certificate will be included in the Clinical Study Report.

10.3.1 Data Entry and Verification

Data will be transcribed from original sources by the PI or designee into the CRF. Data received from external sources, as applicable, will be integrated into the Clinical Data Interchange Standards Consortium study data tabulation model datasets.

10.3.2 Data Validation

After the data have been entered, various edit checks (including manual review of listings) will be performed to ensure the accuracy, integrity and validation of the database against the CRF as described in the DMP.

Inconsistencies that arise from these edit checks will be resolved with the PI or designee.

10.3.3 Database Lock

Upon study completion, after data entry is complete, the data has been pronounced clean, and the PI has reviewed and provided approval via signature, the database will be locked and final write access will be removed.

The Sponsor will be required to provide database lock approval.

Any changes to the data following database lock will be documented and approved by the Sponsor prior to unlocking the database to make changes to the data.

The final transfer of all study data to the Sponsor will be in SAS format with supporting documentation as described in the DMP.

10.4 Direct Access to Source Data/Documents

All CRUs and vendors will ensure that the Sponsor, IRB and inspection by domestic and foreign regulatory authorities will have direct access to all study-related sites, source data/documents, and reports for the purpose of monitoring and auditing (ICH[E6][R2] 5.1.2 & 6.10). In the event that other study-related monitoring should be done by other parties, they will be required to sign a confidentiality agreement prior to any monitoring and auditing.

10.5 Reporting of the Study

10.5.1 Case Report Forms

A CRF is completed for each dosed participant whether or not the participant has completed the study. The PI will assure complete and accurate entries on the forms. Each CRF will be reviewed and signed by the PI. The final signed CRFs will be archived electronically at the end of study in a document repository system. Final CRFs will be provided to the Sponsor in the format and transfer method as decided between Celerion and the Sponsor which will be documented in the DMP.

10.5.2 Record Keeping

Records and documents, including participants' documented informed consent, pertaining to the conduct of this study must be retained by the PI for 15 years after study completion unless local regulations or institutional policies require a longer retention period. No records may be destroyed during the retention period without the written approval of the Sponsor. No records may be transferred to another location or party without written notification to the Sponsor.

It is the responsibility of the Sponsor to inform the PI/Institution as to when these documents no longer need to be retained.

